### **3. General Description of Study Design**

We will conduct a cluster-randomized controlled trial. The clusters are 20 rheumatologists at multisite BWH and MGH-affiliated clinics. Rheumatologists will be stratified by hospital and by gender and randomly assigned. Ten rheumatologists will be assigned to the intervention arm and ten to the control. Assessments will be conducted for 8-10 patients per rheumatologist (max 100 patients total in each arm, 200 total). Randomization will be stratified by BWH and MGH Rheumatology main campus hospitals (MGH or BWH/ Faulkner (FH)) and their rheumatology satellite clinic sites, and by provider gender (male or female). Study schema is included as an attachment.

In addition to the 200 SLE, osteoarthritis, and inflammatory arthritis patients including RA who will be studied directly, we also will examine the medical records of patients with inflammatory arthritis, osteoarthritis, or SLE in the practices of the enrolled providers seen during the same study period. In addition to the chart review of patients who meet the inclusion criteria of less than 2 visits in the past year, we will perform a secondary analysis of all patients who may have been seen greater than 2 times in the past year as we anticipate a spillover effect from the intervention and would like to study

this. Patients who were approached to participate in the audiorecorded component of the trial and declined will not be included in this medical record review. We will have no direct interaction with these patients. Most medical records we will review will be for patients of enrolled providers who we had no direct interaction with. The goal of this chart review component is to more broadly examine the impact of the intervention on the quality measures described in Table 1 below, beyond those individuals who will have their encounters audiorecorded. In addition to allowing for a larger sample size for analysis, it also will allow for analyses that may not be influenced by the act of recording an encounter (e.g., possibly, due to the recording, care may be somewhat different from other patients in each providers' practice and this will allow us to capture both). For quality metrics that would only be a onetime screen or once every few years, we will review prior records to see if they were eligible for those outcomes (such as receipt of vaccinations).

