### 2. Patients

**2A. Identification:** We will identify patients with systemic lupus erythematosus, osteoarthritis, and/or inflammatory arthritis including rheumatoid arthritis, who are scheduled to see the enrolled providers from BWH/FH and MGH rheumatology main hospital clinics and their rheumatology satellite clinic sites. We will do this using a variety of methods including RPDR, EDW and EPIC searches and chart review. We will exclude any individual who has opted out of research and not contact them. Searches will be conducted by research assistants and supervised by the PI and Co-Is.

**2B. Inclusion/Exclusion Criteria:** We will include male and female patients of the participating providers who are able to provide consent, English-speaking,  $\geq 18$  years old, Black or African American or insured by Medicaid/Mass Health (as a proxy for low socioeconomic status), have a diagnosis of SLE, osteoarthritis, or inflammatory arthritis

including RA (or referred to rheumatology because of high suspicion for these conditions), and have been seen  $\leq 2$  times in the past year by the provider. In the past two years, there were  $>7,400$  patients with systemic rheumatic conditions at BWH and  $>5,600$  at MGH; 15% were Black or insured by Medicaid at BWH, 12.4% at MGH. We will exclude patients from the audiorecorded component who are incarcerated or unable to consent. We will exclude any patient from our searches who has opted out of research. If a patient declines to participate in the trial, we will not include them in the medical record review cohort either. However, if a patient of an enrolled provider does not decline participation in the audiorecorded component or is not approached for the audiorecorded component and meets our inclusion criteria, they will be included in our medical record review, along with patients who consent for participation in the audiorecorded component.

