## 2. Patients

Patients who consent to participate will be asked to have one clinical encounter with their provider recorded (preferably the next appointment) and then to complete a set of baseline surveys following that encounter including demographics, social determinants of health, everyday discrimination experiences, satisfaction with care, patient trust in the medical profession, patient perception of care centeredness and medication adherence. Surveys can be completed either via REDCaps via a link sent securely to the patient, or on paper forms (and then will be entered into REDCap by our study team). We will also assess medication adherence again 3 months after the encounter using a survey or a brief phone call, and over the 6-month period using the proportion of days covered data now available in the EMR. Patients will receive a \$30 gift card or e-check once the surveys are completed. We will also collect data from the patients' charts. These data include: demographics, social determinants of health, comorbidities/diagnoses, quality metrics related to their rheumatic disease, lab results, preventive care use (including immunizations), healthcare utilization (including ED visits, hospitalizations, outpatient visits and appointment no shows), medication use (including use of contraception as a quality metric), and medication refill data (proportion of days covered, available in the EMR) over the 6 months following the date of the recorded encounter. We will review the note from the date of the encounter and determine whether the individuation statement was documented in the intervention group.

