## 3. Chart reviews

We will examine the charts of patients with lupus, osteoarthritis, or inflammatory arthritis seen >1 time by enrolled providers in both the intervention and control arms during the 6 months following provider enrollment, beginning  $\geq 1$  month after the date the provider takes the IATs. As indicated above, we will not obtain informed consent for patients of consented providers who will not be audiotaped but whose charts will be reviewed. Patients who were reached and invited to participate in the audiotaped encounter and surveys and did not consent or opted out of participation when approached will not have their chart reviewed. Patients who were not approached, or who were sent letters but could not be reached by phone or in person and did not opt out and are seen during this time frame by providers who are part of this study, may have their charts reviewed. We plan to collect demographics, social determinants of health, comorbidities/diagnoses, quality metrics related to their rheumatic disease, lab results, preventive care use (including immunizations), healthcare utilization (including ED visits, hospitalizations, outpatient visits and appointment no shows), medication use (including use of contraception as a quality metric), and medication refill data over the 6 months following the date of the recorded encounter. We will also see if any of the individuation

statements (smart phrases) were used for patients not specifically enrolled in the intervention (spillover from practice changes by the provider).

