#### 5. Outcomes.

The primary outcome is documented receipt of high-quality care at the time of the appointment or within 30 days of the appointment (see Table 1). The items below will be added together to form a score and the number of items completed out of the total will be the primary outcome measure compared across groups. We will measure these data for all patients with SLE, osteoarthritis, and inflammatory arthritis including RA seen by the provider during the 6-month study period as well as do a separate subgroup analysis focused on the patients who had their appointments audiorecorded. We will use electronic medical record data obtained from chart review, from RPDR and from the Enterprise Data Warehouse (EDW) to obtain these metrics.

Table 1. Quality metrics for diseases of interest		
Systemic lupus erythematosus (SLE)	Rheumatoid Arthritis (RA)	Osteoarthritis
Hydroxychloroquine (HCQ) initiation If lupus nephritis, immunosuppressive initiation, ACE-I or ARB, glucocorticoids Glucocorticoid prophylaxis (e.g. PPI, calcium/vitamin D, PJP if high dose) Contraception if on teratogenic medication Vaccinations Baseline HCQ eye exam and monitoring labs	DMARD initiation, or bDMARD initiation Folic acid if receiving methotrexate Glucocorticoid prophylaxis Contraception if on teratogenic medication Baseline X-rays, TB and hepatitis screening Labs within 1 month of methotrexate initiation Documentation of disease activity measure Vaccinations	Annual functional status assessment Baseline exams Annual pain assessment Recommendation for assistive devices

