#### Secondary outcomes:

- 1) Change in provider IAT scores pre and post intervention. [name] at VCU will participate in this. She will submit to VCU for IRB approval for participation using completely deidentified data. A Data Use Agreement is in process between the two institutions.
- 2) Differences in perception of patient centeredness, patient satisfaction, patient trust in the medical profession, experiences of discrimination and adherence (at time of visit and at 3 months) comparing the intervention to non-intervention group. This secondary outcome is only for that patients enrolled in the study (not the chart review-only non-interaction group). We will additionally measure adherence for a full 6 month period using the proportion of days covered measure now available through the EMR both for participants in the survey component and for the chart review patients.
- 3) Healthcare utilization – we will compare ED visits, hospitalizations, outpatient visits completed and outpatient visit no shows between the two arms in the 6 months following the encounter of interest. We will include chart review patients (non-interaction) as well as patients who consented and had audiorecorded encounters in this part.
- 4) Provider communication (measured only for patients enrolled in the study who had their appointment audiorecorded). Provider communication will be measured using the recorded transcripts and compared between arms: a) physician-to-patient talk time ratio, b) physician word use (number of first person pronouns, and number of positive and negative emotion-related words, divided by all words in the interaction) and c) total length of interaction. This part of the study will be led by [name] (VCU). [name] will have a Data Use Agreement to receive de-identified transcripts for this analysis and separate IRB approval through her institution to work with these deidentified qualitative data.

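### Healthcare utilisation is collected only after the encounter; a pre-randomisation count from the same records would add precision and guard against chance imbalance across 20 providers

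*Combined protocol and SAP*

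**What the plan says.** Secondary outcomes, item 3, sets utilisation as a direct comparison of arms over the half-year after the encounter: "outpatient visits completed and outpatient visit no shows between the two arms in the 6 months following the encounter of interest". Both cohorts count: "We will include chart review patients (non-interaction) as well as patients who consented and had audiorecorded encounters in this part".

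The data lists agree. Section 6.2 (Patients) lists "healthcare utilization (including ED visits, hospitalizations, outpatient visits and appointment no shows" among the chart items and closes the list with "over the 6 months following the date of the recorded encounter". Section 6.3 (Chart reviews) ends its parallel list with "medication refill data over the 6 months following the date of the recorded encounter", although chart-review-only patients have no recorded encounter. In both lists the time phrase could be read as attached to refill data alone, but item 3 settles the window for utilisation.

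Earlier records are already in use. Eligibility depends on the number of "times in the past year by the provider" (Section 4, 2B). For one-time quality items, Section 3 says "we will review prior records to see if they were eligible for those outcomes (such as receipt of vaccinations". The quality metrics draw on "electronic medical record data obtained from chart review, from RPDR and from the Enterprise Data Warehouse (EDW".

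Section 9 states GEE models for the quality score, the communication metrics and the survey scores, and none for utilisation. Its covariates are hospital plus any factor that either correlates strongly with the outcome or differs between arms; rheumatic disease is given as an example of the first kind.

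**The concern.** Ten providers per arm are randomised, stratified only by site and provider gender, and patients follow their provider. Patient case mix can therefore differ between arms by chance, and a few heavy users of care in one practice can move the arm means for admissions or missed visits. A patient's earlier use of care is a plausible predictor of later use. The Section 9 rule looks for exactly such predictors, yet this one is not planned to be extracted and so could not be entered.

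At stake is a wider interval than the records allow, and no direct way to see or adjust for a starting difference in utilisation. This is a secondary outcome for which the plan makes no power claim.

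**Working it through.** **Inputs from the protocol.** 10 providers per arm; ICC 0.02 with 8 patients per provider, or 0.05 with 10; two-sided alpha 0.05; difference 0.5 SD; stated power 84% for the quality score (Section 9). No figure is given for utilisation.

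**Assumptions.** The correlation r between prior and later use is 0.3 to 0.7. The quality-score ICC is borrowed for utilisation. The number of patients per provider, m, is 10 to 50, because chart-review patients are included and their number is not stated. For orientation only, Section 4 gives 7,400 × 0.15 + 5,600 × 0.124 = 1,804 Black or Medicaid-insured patients over two years across 47 + 27 = 74 rheumatologists, or about 24 each. That covers all systemic rheumatic conditions and a longer period than the study.

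**The plan's own figure.** Effective n per arm = 10m / (1 + (m − 1) × ICC).
- m = 8, ICC 0.02: 80 / 1.14 = 70.2; SE = √(2/70.2) = 0.169; 0.5/0.169 − 1.96 ≈ 1.00; power 84.2%.
- m = 10, ICC 0.05: 100 / 1.45 = 69.0; SE = 0.170; power 83.6%.

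Both agree with 84%, so the power statement is not at issue and the same cluster structure can be used below.

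**Variance saved by adjustment.** The variance of a provider mean, in SD² units, is v0 = ICC + (1 − ICC)/m.
- If prior use explains only differences within a provider: v1 = ICC + (1 − ICC)(1 − r²)/m, a saving of r² × [(1 − ICC)/m] / v0.
- If it also explains differences between providers: v2 = v0(1 − r²), a saving of r² for any m.

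At ICC 0.05 the bracketed share is 0.095/0.145 = 0.655 (m = 10), 0.0396/0.0896 = 0.442 (m = 24) and 0.019/0.069 = 0.275 (m = 50).

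| r | within only, m = 10 | m = 24 | m = 50 | both levels, any m |
|---|---|---|---|---|
| 0.3 | 5.9% | 4.0% | 2.5% | 9% |
| 0.5 | 16.4% | 11.0% | 6.9% | 25% |
| 0.7 | 32.1% | 21.7% | 13.5% | 49% |

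**Chance imbalance.** If prior use has the same ICC, the baseline difference between arms has SD √(2 / effective n). The probability of a gap above 0.2 SD is:
- m = 8, ICC 0.02: SD 0.169, probability 24%.
- m = 24: 7% (ICC 0.02) or 14% (ICC 0.05).
- m = 50: 2% (ICC 0.02) or 9% (ICC 0.05).

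Unadjusted, a 0.2 SD gap shifts the estimated arm difference by r × 0.2 = 0.06, 0.10 or 0.14 SD for r = 0.3, 0.5 or 0.7.

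**Where the window must end.** Intervention providers choose their questions and get weekly reminders from training onward (Section 6.1). Recording starts at least 1 month after the IATs, and recruitment is estimated at 6 months. Patients may have seen the provider up to twice in the past year, and Section 6.3 takes chart-review patients seen more than once in the study period. A patient indexed in month 5 may therefore have seen a trained provider in month 2. A look-back from the encounter would include exposed time; one that ends before randomisation would not.

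**The case against.** The strongest reply is that little is lost. Randomisation keeps the comparison unbiased on average, and a clustered standard error already carries chance differences between practices. Section 9 also lets the analyst add any strong predictor. The outcome is an unpowered secondary one in a pilot, and the gain shrinks as the chart-review cohort grows.

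Most of this stands. A reader might infer that post-encounter data cannot distinguish an effect from case mix, so that the comparison is invalid. The documents do not support that: the loss is in precision and in protection from an unlucky allocation. A reader might also infer that Section 9 shuts out prior utilisation. It does not; its strong-correlation criterion would admit it. What the reply does not meet is that no section plans to extract the variable and no utilisation model is stated, so the permission cannot be used as the plan is written.

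The six months before each encounter may look like the natural baseline. Because patients can meet a trained provider before that encounter, such a count could itself be affected by the intervention, and adjusting for it could remove part of the effect.

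There are also limits on r. New referrals have little in-system history, the cap on past visits to the provider weakens r for outpatient visits, and a window ending before randomisation is further from the outcome period.

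**Conclusion.** The point holds as an optional, low-cost improvement. Utilisation is measured only after the encounter, prior utilisation is not planned to be extracted although earlier records are already searched, and no utilisation model is given. The forgone variance reduction at ICC 0.05 and 10 to 50 patients per provider is about 2.5-9% (r = 0.3), 7-25% (r = 0.5) or 13.5-49% (r = 0.7). The lower ends assume that prior use explains only within-provider variation at m = 50; the upper ends assume that it acts at both levels. Figures based on the 8 to 10 recorded patients alone would overstate the lower ends, since this outcome also covers chart-review patients.

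The range rests on an assumed r, an ICC borrowed from the quality score, and a linear approximation for counts that will often be zero. It does not show that the planned comparison is biased or that the 84% power statement is wrong.

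**What to change.** 1. In Sections 6.2 and 6.3, extract the same four counts (emergency visits, hospitalisations, completed outpatient visits, missed appointments) for a fixed window, for example 6 or 12 months, ending before the provider's randomisation and IAT date. Do this in both arms, for recorded and chart-review patients.
2. In Section 6.3 and Secondary outcomes, item 3, define the index date for chart-review-only patients, for example the first qualifying visit in the study window.
3. In Section 9, state a provider-clustered count model for each utilisation outcome, with the matching prior count and an indicator for patients with no prior in-system record as prespecified covariates. Fix this before outcome data are seen.

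The cost is a wider date range in the planned record extraction and two covariates per model. The team should confirm that the HIPAA waiver (Section 7), requested for data needed for outcome evaluation, covers the earlier dates, given the rule in Section 11 that only necessary data be collected. Care outside the health system will be missed before the encounter as it is after, and data will be sparse for new referrals.

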#### 6. Data sharing

De-identified provider IAT data and de-identified transcripts of the patient-provider encounters will be sent via the MGB secure file transfer system to [name] at VCU. She will have her own IRB approval to analyze these data and a Data Use Agreement is in process.

### 7. Risks and Discomforts

Providers may feel uncomfortable learning about the possibility of exhibiting a bias or prejudice not consciously recognized. They may also feel uncomfortable having patient-provider encounters audiotaped. However, the implicit bias literature demonstrates that real-time records (either audio or video) are superior to post-interaction interviews with patients and physicians because self-reports of behavior are often biased and incorrect. Both audio and video recording have been done extensively before and the acceptability of both has been demonstrated by a leading bias researcher (Penner et al. J Nonverbal Behav DOI 10.1007/s10919-007-0024-8, 2007). In this study 85% of patients approached were willing to be videotaped as well. In our study, we are minimizing risk by audiorecording only and not videotaping and all analyses will be conducted using de-identified transcripts. Similarly, patients will be linked with providers using unique identifiers and providers will be deidentified that way too. If providers feel uncomfortable with the aggregate results of the implicit bias association tests, they will have the opportunity to meet with the research team and be linked to resources and trainings through Harvard and MGB to help address these. Patients may also feel uncomfortable answering the survey questions. The informed consent outlines that their responses will not be seen by their treating rheumatologist and all findings will be deidentified before analysis. The study PI will be available to participants to discuss any concerns that arise.

In the pilot trial, we do not anticipate the occurrence of any incremental adverse events as a result of providers receiving training about implicit bias, or for the individuation intervention to improve care for patients with lupus, osteoarthritis, or RA. Providers have ultimate oversight and continue to make all of the care decisions, but those in the intervention arm may elicit additional information to help guide their care and overcome their biases. The study team will not be providing any direct care to patients, and all treatment decisions will ultimately be made by the patients' medical teams at MGB. Any adverse events will be handled in the course of regular clinical care. We will also request a HIPAA waiver of patient authorization to access the her data necessary for outcome evaluation for individuals not participating in the provider-patient recording and survey component, and who did not decline participation in the recording/survey part.

Data for the study will be safeguarded by state-of-the-art security protocols. The facilities have 24-hour security and are protected by locked entrances. MGB has computer networks in place that employ up to date virus protection software and enable password protected access only to study investigators. The setup for analysis of these data will be the same as all the other IRB applications that our MGB research division submits for secondary use of data. In fact, we have an umbrella-approval place in place with the MGB IRB for using these types of HIPAA-limited data. All the datasets, including limited protected health information (PHI), will be stored only on secure servers at MGB's data center and will only be accessed by a limited number of individuals in the study team from this division who are all trained in data security and patient privacy. To ensure the confidentiality and security of all data, the research team operates a secure, state-of-the-art computing facility housed at MGB's data center. The MGB data center is a secure facility that houses both computing environments as well as clinical systems and electronic medical records for several large hospitals in Eastern Massachusetts. Entry into the computer room requires staffed computer room security. The Division's computers are connected to the MGB networking backbone with 10 gigabit-per-second fiber links. Network security is overseen by electronic medical records systems to the research team's data. All data are transmitted to programmers' workstations in an encrypted state. Backups are created using 256-bit AES encryption, the current Department of Defense standard for data security, and are stored in a locked facility. The redundancy, extensive data power, and security of our computer facility confirm our capacity to collect and manage data and ensure confidentiality for all project participants.

